13.2 Analysis of the data

Continuous variables will be reported as median and interquartile, because of potential deviation from Gaussian distribution. Discrete variables will be reported as N and %. For the primary endpoint, the comparison in the interval change in LDL cholesterol between alirocumab and placebo will be completed using an ANOVA for repeated measures and assessing the P value for time_x_group allocation. P values <0.05 will be considered significant. Missing data will not be input. For the purpose of safety analysis, all patients receiving the investigational drug will be considered, independent of missing data.

14) REFERENCES

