Alirocumab in Patients with Acute Myocardial Infarction

A Randomized Controlled Double-Blinded Study

The VCU Alirocumab Response Trial

STUDY PROTOCOL

Principal Investigator: [name], PhD

Sponsor: Virginia Commonwealth University

Funding provided by: Regeneron Pharmaceuticals, Inc. and
Sanofi U.S.

TABLE OF CONTENTS

- 1) PERSONNEL**
- 2) PROTOCOL SUMMARY**
- 3) BACKGROUND INFORMATION AND SCIENTIFIC RATIONALE**
- 4) OBJECTIVES**
 - 4.1 Study objectives
 - 4.2 Study outcome measures
 - 4.3 Study endpoints
- 5) STUDY DESIGN**
- 6) ENROLLMENT IN THE STUDY**
 - 6.1 Inclusion criteria
 - 6.2 Exclusion criteria
- 7) RANDOMIZATION**
- 8) TREATMENT WITH THE INVESTIGATIONAL DRUG**
- 9) STUDY ASSESSMENT**
- 10) POTENTIAL BENEFITS AND RISKS**
 - 10.1 Alirocumab
 - 10.2 Social and psychological risks
 - 10.3 Testing Risks
 - 10.4 Direct benefits to study participants
- 11) ASSESSMENT OF SAFETY**
 - 11.1 Reporting of Adverse Events
- 12) DISCONTINUATION OF TREATMENT AND WITHDRAWAL**
- 13) STATISTICAL CONSIDERATIONS**
- 14) REFERENCES**

1) PERSONNEL

Name	Role	Institution/ Division
[name], PhD	Principal Investigator	VCU, Cardiology
[name]	Regulatory Coordinator	VCU, Cardiology
[name]	Investigator	VCU, Cardiology
[name] [name]	Investigator	VCU, School of Pharmacy
[name], MS	Investigator	VCU, Cardiology
[name]	Investigator	VCU, School of Pharmacy
[name], MS	Investigator	VCU, Cardiology
[name]	Investigator	VCU, Internal Medicine
[name]	Investigational Pharmacy	VCU, School of Pharmacy

2) PROTOCOL SUMMARY

- Title:** **Alirocumab in Patients with Acute Myocardial Infarction**
- Population:** 20 patients aged ≥ 21 years presenting with an acute spontaneous non-ST elevation myocardial infarction (NSTEMI) who are already taking at least moderate intensity statin therapy at time of hospital admission
- Description:** Phase IV clinical trial of the alirocumab, an inhibitor of the proprotein convertase subtilisin/kexin (PCSK9), or placebo added to high-intensity statin (atorvastatin 80 mg) in LDL cholesterol lowering during NSTEMI.
- Objectives:** To determine the effectiveness of alirocumab in further lowering cholesterol LDL and inflammatory biomarkers when initiated acutely in patients with NSTEMI, in addition to high intensity statin, atorvastatin 80 mg.
- Primary Endpoint:** Placebo-corrected percentage change in calculated LDL cholesterol from baseline to day 14.

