4.1 Study Objectives

We propose to study the effects of early initiation of alirocumab in addition to high intensity statin therapy in patients who have previously been treated with moderate-high intensity statins, who present with a type I (spontaneous) acute non-ST segment elevation MI (NSTEMI). Particular attention will be paid to additional LDL lowering effects, as well as the effects on PCSK9 levels and inflammatory biomarkers.

Biomarkers will be collected at baseline, 3 days, and 14 days after randomization.

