4.3 Study Endpoints

Primary Endpoint:

[figure not shown]
- Placebo-corrected percentage change in calculated LDL cholesterol from baseline to day 14.

Secondary Endpoints:

- Placebo-corrected percentage change in calculated LDL cholesterol from baseline to 72 hours;
- Placebo-corrected percentage change in PCSK9 levels from baseline to 72 hours and 14 days;
- Placebo-corrected percentage change in Lp(a) levels from baseline to 72 hours and 14 days;
- Placebo-corrected percentage change in inflammatory markers (hsCRP, IL-6, IL-10, and TNF- α) from baseline to 72 hours and 14 days;
- Safety and tolerability of alirocumab when initiated in the inpatient setting soon after an NSTEMI.

5) STUDY DESIGN

We designed an active-controlled, double-blinded study of alirocumab versus placebo in addition to high intensity statin, atorvastatin 80 mg, in patients who present with acute type I (spontaneous) NSTEMI and who are already taking a moderate-high intensity statin prior to admission.

The study is composed of two treatment arms exploring:

- a) Alirocumab 150 mg given as a single dose subcutaneously + Atorvastatin 80 mg orally daily;
- b) Matching placebo injection subcutaneously + Atorvastatin 80 mg daily.

6) ENROLLMENT IN THE STUDY

Patients who are admitted to the Pauley Heart Center in the VCU Medical Center will be screened for inclusion and exclusion criteria based on a cursory evaluation of the information available in their medical charts. This approach is supported by a partial waiver of informed consent for authorization to access protected health information to allow identification of the subjects. After identifying the potential subjects, the investigators will approach the subjects in a private manner and review the informed consent form approved by the Institutional Review Board. Any additional information about their medical history that is unclear or incomplete from the medical charts will be clarified by speaking with the patients and obtaining confirmatory outside medical records, with the consent of the patients, if deemed necessary.

Patients agreeing to participate in the study will sign the informed consent form and will be given a copy of the consent form signed by the investigator performing the informed consent process. No study procedures will occur prior to the subject signing the approved informed consent.

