6.1 Inclusion Criteria

Both criteria must be met for enrollment of the patient into the study

- 1) Acute type I (spontaneous) non-ST elevation AMI defined as chest pain (or equivalent) with an onset of symptoms within 12 hours of presentation, a duration of >15 minutes, and elevated cardiac troponin I levels, with or without electrocardiographic changes [with the exclusion of ST elevation];
- 2) On medical therapy with moderate-high intensity statin prior to admission (either atorvastatin 20, 40 or 80 mg, or simvastatin 20, 40 or 80 mg or rosuvastatin 20 or 40 mg) as documented by hospital or pharmacy records and with known LDL cholesterol ≥ 70 mg/dL within the prior 12 months.

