The Investigational Pharmacist ([name], RPh) who will not be involved in patient care, data gathering, or data analysis, will be in charge of randomization. Patients will be randomized 1:1 to Alirocumab 150 mg or placebo.

Access to randomization log will be restricted and allowed only on an emergency basis, or at the end of the study including all data collection. In case of an emergency, a physician treating any patient enrolled in the study may request un-blinding of that individual patient if the physician determines that un-blinding is necessary to make a treatment decision. The PI will contact the VCU Investigational Pharmacy to provide the treatment allocation to the PI, who will then relay the information to the treating physician. Upon completion of the study (including completion of all data collection and event adjudication), the PI will request the complete randomization log from the VCU Investigational Pharmacy.

8) TREATMENT WITH THE INVESTIGATIONAL DRUG

After signing of the informed consent, verification of the inclusion/exclusion criteria, obtaining baseline laboratory samples, and randomization, patients will receive their

injection of either alirocumab 150 mg or matching placebo administered subcutaneously. The dose will be administered by a nurse or an investigator appropriately using a dedicated auto-injector. The syringes and auto-injectors are prepared in a manner in which the active drug will be indistinguishable from the placebo, to ensure blinding of the providers and subjects.

To avoid prescribers prescribing additional PCSK9 inhibitors during the study, we will write a note in the clinical chart of each study subject informing providers about the enrollment in the study and the recommendation to not prescribe PCSK9 inhibitors until completion of the trial protocol (2 weeks). This will avoid patients being treated with two different PCSK9 inhibitors or with overlapping doses of alirocumab.

9) STUDY ASSESSMENTS

	Baseline (Day 0)	Day 3 (Or Discharge)	Follow Up (14 ± 3 days)
Screening	X		
Consent	X		
Administer Med	X		
History	X		X
Physical Exam	X		X
Medication List	X	X	X
Biomarkers	X	X	X

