Patient will have blood samples (approximately 30 mL) drawn at baseline after signing the informed consent form but before receiving the study injection. The panel of biomarkers will include a lipid panel (total cholesterol, LDL-C, HDL-C, triglyceride levels, and Lp[a]), PCSK9 levels, inflammatory biomarkers (including hsCRP, IL-6, IL-10, and TNF- α), complete blood count (CBC), and complete metabolic panel (CMP).

After 3 days, or at the time of patient discharge (whichever occurs first), blood samples (approximately 30 mL) will be drawn again to re-measure the biomarkers listed above, and the patient will be given an appointment for a visit 14±3 days from enrollment. At their follow up visit, patients will undergo a repeat history and physical exam, and blood samples (approximately 30 mL) will again be drawn to re-measure the biomarkers listed above. This will complete the participation of the subjects in the clinical trial. The patient's clinical care will then continue on a regular basis, according to standard of care.

Biomarkers will be measured by LabCorp (Cincinnati, OH). The tubes will be collected by trained personnel, and immediately inverted 8-10 times after being drawn. Samples are then processed, refrigerated and shipped within 24 hours. The results from LabCorp will be sent securely to the PIs and designated investigators by email and/or fax.

For the measurement of the PCSK9 levels, not available commercially, we will collect samples, process them, and store them in a freezer located our lab for single batch analysis by Regeneron Pharmaceuticals, Inc. and Sanofi U.S.

10) POTENTIAL BENEFITS AND RISKS

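### The primary LDL comparison subtracts baseline but does not use it as a covariate; with 10 patients per arm this costs some precision, not validity

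*Combined protocol and SAP*

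**What the plan says.** The primary endpoint in Section 4.3 is "Placebo-corrected percentage change in calculated LDL cholesterol from baseline to day 14". Section 13.2 gives the analysis: "the comparison in the interval change in LDL cholesterol between alirocumab and placebo will be completed using an ANOVA for repeated measures", "assessing the P value for time_x_group allocation". It does not say whether the interval change is in mg/dL or in percent, names no covariate, and mentions a P value but no estimate with an interval.

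Three other places bear on the point.

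- **Baseline is measured in everyone.** Section 9 has blood "drawn at baseline after signing the informed consent form but before receiving the study injection", and Section 4.1 adds later visits: "Biomarkers will be collected at baseline, 3 days, and 14 days after randomization".
- **Randomization does not balance LDL.** Section 7 says only "Patients will be randomized 1:1 to Alirocumab 150 mg or placebo"; no stratification on LDL appears. The Protocol Summary sets the size at 20 patients, so 10 per arm.
- **Entry does not fix LDL at randomization.** Section 6.1 asks for statin treatment "with known LDL cholesterol ≥ 70 mg/dL within the prior 12 months". That sets a lower limit on a past value and no upper limit.

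**The concern.** When baseline is one of the repeated measures, the baseline-to-day-14 part of the time-by-group interaction is a comparison of change scores. A change score uses baseline by subtraction, which assumes that a patient who starts 1 mg/dL higher ends 1 mg/dL higher. If the true slope is lower, the arm that happens to start higher appears to fall further, and part of the chance imbalance passes into the estimated drug effect. In a trial of 10 per arm without stratification, such imbalance can be sizeable. A covariate lets the data set the slope and removes this dependence. At stake is the precision of the primary estimate, and how far a reader must discount it when the arms start at different LDL.

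**Working it through.** **1. The plan's own power.** Section 13.1 takes a 40-point difference, SD 25% and 20 patients. The standard error is 25 × √(2/10) = 11.18, and 40/11.18 = 3.578. Two-sided normal power is Φ(3.578 − 2.576) = 84.2% at alpha 0.01 (the level in 13.1) and Φ(3.578 − 1.960) = 94.7% at 0.05 (the level in 13.2). By t test these are 74.8% and 92.2%. The stated power above 99% at 0.01 does not reproduce with 20 patients in total; 20 per arm would give 99.4%. That is a separate matter, but it means the plan has less power in reserve than it states.

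**2. Dependence on chance imbalance.** Let σ be the SD at both visits and ρ the baseline/day-14 correlation.

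- Variance of the change: 2σ²(1 − ρ). Residual variance after adjustment: σ²(1 − ρ²). Ratio: (1 + ρ)/2, which is 0.65, 0.75, 0.85 and 0.95 at ρ = 0.3, 0.5, 0.7 and 0.9.
- Correlation of the change-score estimate with baseline imbalance: −√((1 − ρ)/2), which is −0.59, −0.50, −0.39 and −0.22. After adjustment it is zero.
- The documents give no baseline SD. For an assumed 20, 30 or 40 mg/dL, the standard error of the baseline difference is SD × √(2/10) = 8.9, 13.4 or 17.9 mg/dL. A one-standard-error imbalance leaves (1 − ρ) times that in the change difference: 2.7 mg/dL (SD 20, ρ = 0.7) to 12.5 mg/dL (SD 40, ρ = 0.3). That is 2% to 10% of the 124 mg/dL expected in 13.1.

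**3. Gain on the declared percentage-change scale.** Simulation, 10 per arm; assumed log-normal LDL, placebo −10% and alirocumab −50%; coefficient of variation (CV) and correlation as shown.

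| CV, correlation | SD of % change | Power unadjusted, 0.05 / 0.01 | Power adjusted, 0.05 / 0.01 | Fall in SE |
|---|---|---|---|---|
| 30%, 0.3 | about 27% | 93% / 75% | 98% / 88% | about 13% |
| 30%, 0.5 | about 22% | 98% / 90% | 99% / 95% | about 8–9% |
| 40%, 0.7 | about 23% | 98.1% / 88.7% | 98.5% / 90.3% | about 4% |
| 45%, 0.8 | about 20% | 99.5% / – | 99.4% / – | near 0 |

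Before rounding, the first row gains about 4 points at 0.05. At correlation 0.9 there is no gain. In the 30% CV settings, type I error was about 5% with and without adjustment.

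A simpler check keeps the plan's SD of 25% and uses a residual SD of 25 × √(1 − r²), where r is the size of the correlation between baseline and percentage change. At r = 0, 0.3 and 0.5 the t-test power at 0.05 is 92.1%, 94.2% and 97.3%, against 92.2% unadjusted. This is slightly favourable to adjustment, because it charges the lost degree of freedom but not the cost of estimating the slope.

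**4. If interval change means mg/dL.** With CV 30% and correlation 0.3–0.5, the unadjusted mg/dL change has 77–88% power at 0.05, and adding baseline LDL alone raises this to about 99%.

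**5. The three-visit test.** A separate mg/dL simulation used a change SD of 31 (25% of 124), a day-14 effect of 49.6 (40% of 124), an assumed day-3 effect of 20 and correlation 0.5. Power at 0.05 was 87.6% for the three-visit interaction, 91.8% for the day-14 change score and 96.3% for ANCOVA. Only the step from 91.8% to 96.3% is due to the covariate. The first step arises because the three-visit interaction has 2 degrees of freedom and is not specific to day 14.

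**The case against.** The planned method is valid. It uses each patient's baseline, holds its type I error, and is unbiased over repeated randomizations. All of this stands, so the point concerns efficiency and freedom from chance imbalance.

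The size rests on quantities that the documents do not give. The plan's SD of 25% does not identify them: CV 30% with correlation 0.3–0.5 and CV 40% with correlation 0.7 both give an SD near it, yet the gain differs from about 4 points to almost none. This also stands, and the range must reach zero.

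A reader might infer that the plan gives up 10 to 20 points of power, by setting an mg/dL change score against an adjusted percentage or log model. The documents do not support that. Section 13.2 does not say that the change is in mg/dL, and Section 4.3 declares a percentage. The objection goes too far only if it puts that whole gap down to scale, since on the mg/dL scale the covariate alone recovers most of it.

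A reader might also infer from the open upper limit on LDL that baseline spread will be wide. That is plausible, but no baseline SD is given and Section 6.2 excludes homozygous familial hypercholesterolemia.

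**Conclusion.** The omission is real and worth correcting. Without a baseline covariate, the primary estimate keeps a correlation with chance baseline imbalance that adjustment would remove. On the declared percentage-change scale, with CV 30–45% and correlation 0.3–0.9 assumed, adjustment lowers the standard error by about 0–13% and adds about 0–4 points of power at 0.05, or 0–13 points at 0.01. The gain is larger on the mg/dL scale and vanishes on the percentage scale at high correlation. It would be wrong to conclude that the planned test is biased, that its error rate is inflated, or that the trial's answer depends on this choice. If the effect is near 40 points, significance will probably be reached either way, and the benefit is mainly a tighter estimate that does not shift with the baseline draw.

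**What to change.** In Section 13.2, make the primary comparison an ANCOVA of percentage change in LDL at day 14 on arm, with baseline LDL as covariate. Report the adjusted difference with its confidence interval. This matches the endpoint in 4.3 and the effect in 13.1, and it settles the unit of the interval change.

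Log day-14 LDL adjusted for log baseline is an acceptable alternative, but it estimates something else. With −10% and −50%, the ratio of geometric means is 0.5/0.9 − 1 = −44%, against a difference of 40 points. If it is chosen, 4.3 and 13.1 should say that the effect is a ratio of geometric means.

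Use the same model for 72-hour LDL, Lp(a) and PCSK9; Section 13.2 names a model only for the primary endpoint. The cost is one residual degree of freedom and aligned wording, with no new patients or data. The change should be made before the randomization log is released.

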4.2 Study Outcome Measures

LDL cholesterol levels. We will administer one dose of alirocumab 150 mg subcutaneously in addition to atorvastatin 80 mg given as standard of care, then monitor the change in LDL cholesterol at baseline, 3 days, and 14 days when compared to control subjects who receive placebo in addition to atorvastatin 80 mg.

PCSK9 levels. PCSK9 levels will also be measured at each time point, to monitor the effectiveness of alirocumab in lowering those levels when initiated acutely during an NSTEMI. We expect PCSK9 levels to rise with high intensity statin treatment alone but be lowered by treatment with alirocumab.

Lipoprotein(a). Levels of lipoprotein(a) [Lp(a)], another well-validated cardiovascular risk marker, will be measured at each time point. We expect a marked reduction in Lp(a) levels, as was observed in prior trials using alirocumab.

Inflammatory biomarkers. High-sensitivity C-reactive protein (hsCRP), interleukin-6 (IL-6), IL-10, and tumor necrosis factor- α (TNF- α) will be measured at each time point. We expect an inflammatory response after an NSTEMI, with a peak in many of the markers at 72 hours after the onset of symptoms. We suspect that treatment with alirocumab may blunt this inflammatory response.

Safety and tolerability. Although Alirocumab is already approved as an adjunct to diet and maximally tolerated statins for the treatment of patients with familial hypercholesterolemia and for patients with clinical atherosclerotic cardiovascular disease who require additional lowering of LDL-cholesterol, the current study represents the first clinical trial in which alirocumab will be given in patients with acute NSTEMI in the inpatient setting. Subjects will be screened for any adverse side effects or events thought potentially related to alirocumab treatment immediately after administration of the study injection, at 3 days, and at 14 days after the dose. A complete blood count with differential and complete metabolic panel will be drawn at each time point, as well.

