- The sponsor shall be responsible for ensuring submission of required expedited and periodic reports to the appropriate Regulatory Authority (RA), the Ethics Committee and investigators of each country participating in the Investigator-Sponsored Study (ISS, based on applicable regulations).
- Any Periodic reports (e.g. Development Safety Update Report (DSUR)), submitted to Regulatory Authority must first be transmitted to Regeneron/Sanofi for review and comment
- The Sponsor must provide to Regeneron/Sanofi any New Safety Findings pertaining to safety of the Investigational product within one (1) business day (e.g. Data Safety Monitoring Board recommendations).

12) DISCONTINUATION OF STUDY PARTICIPATION AND WITHDRAWAL

Patients may withdraw from the study at any time. The patient can decide to forgo any study procedures that makes him/her uncomfortable or wish not to complete. The study doctor may however stop the participation of the patient in this study at any time for many reasons including (*but not limited to*) the study doctor thinks it is necessary for patient health or safety, the patient has not followed study instructions, or administrative reasons requiring withdrawal.

Loss to follow-up can occur due to patients' withdrawal or death. If patients are lost to follow up and their clinical condition cannot be established (alive vs dead, hospitalized vs not), they will be excluded from the initial analysis, and then reintroduced for sensitivity analysis considering all potential outcomes. A 10% attrition rate is a reasonable assumption.

13) STATISTICAL CONSIDERATIONS

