13.1 Sample Size

In the ODYSSEY Long Term trial, the addition of alirocumab 150 mg to maximally tolerated statin therapy resulted in a reduction of LDL cholesterol of approximately 60% at 4 weeks⁵. Similar LDL reductions were seen even when used in statin-intolerant

patients, as demonstrated in the ODYSSEY Alternative trial²⁴. We anticipate that patients will have baseline LDL levels of approximately 124 mg/dL on first presentation², and that a >40% in LDL reduction will be observed after treatment with alirocumab + atorvastatin 80 mg on top of what is seen with placebo + atorvastatin 80 mg at 2 weeks (primary endpoint), with a standard deviation of approximately 25%. These estimates lead to a predicted power >99% ($\alpha=0.01$) with a sample size of 20 patients, and of >95% with a 25% loss to follow up at 14 days. We also expect that patients with an acute myocardial infarction to have increased CRP levels, peaking at 72 hours^{22,23}. A sample size of 20 patients will also provide a power of 65-85% to detect a reduction of 33-50% in CRP or IL-6 plasma levels at 72 hours or 14 days with alirocumab + atorvastatin 80 mg on top of placebo + atorvastatin 80 mg (secondary endpoint).

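### Section 13.2 tests the day-14 LDL endpoint by a time x group P value without naming the visits or the percentage scale, and plans no between-arm estimate with a confidence interval

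*Combined protocol and SAP*

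**What the plan says.** The protocol summary (section 2) and section 4.3 give the primary endpoint as "Placebo-corrected percentage change in calculated LDL cholesterol from baseline to day 14". Section 4.3 lists a separate secondary endpoint: "Placebo-corrected percentage change in calculated LDL cholesterol from baseline to 72 hours".

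LDL is measured three times. Section 4.2 plans to "monitor the change in LDL cholesterol at baseline, 3 days, and 14 days when compared to control subjects who receive placebo". Section 9 fixes the middle draw only loosely: "After 3 days, or at the time of patient discharge (whichever occurs first), blood samples" are taken.

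Section 13.2 says that the primary comparison of the two arms, described only as one of interval change, "will be completed using an ANOVA for repeated measures and assessing the P value for time_x_group allocation". The threshold is P below 0.05, with no statement of sidedness. Continuous variables are summarised as medians with interquartile ranges because they may not be normally distributed, and missing values are not imputed. The section does not list the visits in the model, use the word percentage, name a day-14 contrast, or plan a between-arm difference with a confidence interval.

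Section 13.1 sizes the trial on a reduction of more than 40% "on top of what is seen with placebo + atorvastatin 80 mg at 2 weeks (primary endpoint), with a standard deviation of approximately 25" percent. It gives no effect or SD for day 3. For patients lost to follow-up whose clinical status is unknown, section 12 says "they will be excluded from the initial analysis, and then reintroduced for sensitivity analysis considering all potential outcomes".

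**The concern.** A time x group P value answers different questions depending on how many visits are in the model. With baseline and day 14 it tests exactly the endpoint. With all three visits it tests whether the arms differ in LDL course at either later time, so a secondary endpoint feeds into the primary P value and P < 0.05 does not by itself show a day-14 effect. Two analysts could both follow section 13.2 and run different primary tests. If the choice were made after seeing the data, the primary P value would no longer be fully prespecified.

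The choice can also change who is analysed. Without imputation, a conventional three-visit ANOVA drops a patient who missed the day-3 draw even when day-14 LDL is available.

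Separately, the endpoint is an effect size, while the plan commits only to a P value and within-arm spread. With 20 patients, the precision of the between-arm difference is what a reader most needs.

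**Working it through.** **Inputs from the documents.** 20 patients, 1:1, so 10 per arm (sections 2 and 7); 40 points at day 14 and SD 25 points for the 2-week change (section 13.1); alpha 0.05 (section 13.2), taken as two-sided.

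**Assumptions.** The documents give no day-3 effect, no day-3 SD and no correlation between the day-3 and day-14 changes. I take a day-3 effect of 20 points, a day-3 SD of 10 to 35 and a correlation r of 0.3 to 0.7. Changes are simulated as bivariate normal.

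**The plan's own power figure.** Section 13.1 states more than 99% power at alpha 0.01 with 20 patients. With 10 per arm, 40 points and SD 25, two-sided power is 84.2% (normal) or 74.8% (noncentral t), so the figure does not reproduce. It matches 20 per arm (99.35%, normal). That is a separate matter and nothing below depends on it. At alpha 0.05, noncentral t gives 92.2%, the benchmark used here.

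**Two visits.** The interaction compares mean change between arms. F has 1 and 18 df and equals the square of the t statistic on change, so P is identical. With no day-14 effect it rejects in about 5% of trials whatever happens at 72 hours.

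**Three visits.** The interaction has (3 - 1) x (2 - 1) = 2 df, with error df 2 x (20 - 2) = 36. The null hypothesis is no difference at day 3 and none at day 14. The statistic depends on the data only through each patient's changes from baseline, so simulating the two changes is enough.

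Uncorrected F against the t test on day-14 change, 10 v 10:

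| Scenario | Day-3 SD 25, r = 0.3 / 0.5 / 0.7 | Day-3 SD 10 to 35, r 0.3 to 0.7 |
|---|---|---|
| 20 at day 3, 40 at day 14: omnibus power (day-14 test 92%) | 85 / 88 / 90% | about 70 to 95% |
| Same: day-14-significant trials with omnibus P >= 0.05 | 8.9 / 5.6 / 3.0% | 0 to 24% (14 to 24% at SD 35) |
| Stress case, 20 at day 3, none at day 14: omnibus P < 0.05 (day-14 test 5%) | 36 / 41 / 47% | about 26 to 74% |

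In the first scenario at day-3 SD 25, about 1% of omnibus-significant trials have day-14 P >= 0.05. With 40 points at both visits and SD 25, omnibus power is about 95% against 92%; 5.1 / 4.6 / 4.2% of omnibus-significant trials lack day-14 significance, and 2.4 / 1.6 / 0.7% of day-14-significant trials lack omnibus significance. In the stress case at SD 25, a Greenhouse-Geisser correction gives 34 / 39 / 43%.

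**Precision of the day-14 difference.** Half-width = t(0.975, n1 + n2 - 2) x 25 x sqrt(1/n1 + 1/n2).

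- 10 v 10: 2.101 x 11.18 = 23.5 points
- 9 v 9 (the 10% attrition of section 12): 25.0 points
- 8 v 7 (the 25% loss of section 13.1): 28.0 points

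An observed 40 points at 10 v 10 would have an interval of 40 - 23.5 = 16.5 to 40 + 23.5 = 63.5.

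**The case against.** The strongest reply is that section 13.2 opens by referring to the primary endpoint and speaks of one interval change, and sections 2 and 4.3 define that interval as ending at day 14. On that reading the test is right and nothing is mixed. This stands: it is the closest reading, and the mixing concern applies only if day 3 enters. It does not settle the matter, because LDL is scheduled at three visits, repeated-measures ANOVA is a natural choice for three time points, and section 13.2 does not exclude the middle one. Nor are these the only layouts: the ANOVA could be run on the two change scores, where an equal 40-point effect at both visits would be detected only about 5% of the time.

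A reader might infer that the primary result could come from the 72-hour effect alone. That needs both the three-visit model and no day-14 effect. Section 13.1 expects more than 40% at 2 weeks and cites about 60% at 4 weeks, so the 26 to 74% figure is a stress case and not a forecast.

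A reader might also infer that the omnibus test always costs power, or that the two tests nearly always agree. Neither holds: the answer turns on a day-3 SD that the documents do not give.

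Finally, the plan does report spread, as interquartile ranges, and a placebo-corrected endpoint implies a between-arm difference. Both are true, but spread within each arm is not the precision of the difference. The width of the interval follows from the sample size and SD and is not an error in the test.

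**Conclusion.** The point holds as a gap in specification and reporting. Section 13.2 does not identify one primary test for the day-14 endpoint, does not carry the percentage scale into it, and plans no between-arm estimate with an interval. These omissions apply however many visits enter.

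The consequence for the P value is conditional on day 3 entering. At the planned day-14 effect with an assumed 20 points at day 3, the two tests can disagree by little or by a material amount (0 to 24% of day-14-significant trials), depending on the assumed day-3 SD and correlation. All simulated figures assume normal changes, 10 complete patients per arm and the plan's SD of 25 at day 14. The documents do not support saying that the planned test is invalid or that the 72-hour effect will drive the result. The interval of about ±23.5 points, widening to ±28.0 with 25% loss, rests only on the plan's own SD and patient numbers. It should be fixed, and the change is small.

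**What to change.** State in section 13.2 that the primary analysis is the alirocumab minus placebo difference in percentage LDL change from baseline to day 14, estimated by ANCOVA with baseline LDL as covariate, in all randomised patients with baseline and day-14 LDL whether or not the day-3 sample was drawn. Report it in percentage points with a 95% confidence interval and two-sided P. Because the plan itself expects possible non-normality, add a rank-based or permutation analysis as a sensitivity check. Analyse the 72-hour change in the same way as secondary, and keep the time x group test as descriptive. The section 12 sensitivity analysis can stay.

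Naming the day-14 contrast and its interval closes the gap. The covariate is a refinement, and an unadjusted difference with an interval would also do.

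The cost is wording, no new data, and one degree of freedom. Simulated with mean baseline LDL of 124 mg/dL (section 13.1) and an assumed coefficient of variation of 0.3, power moves from 92.2% unadjusted to 90.4% if baseline does not predict percentage change, 92.8% at correlation 0.3 and 96.4% at 0.5. The mean interval half-width is 23.9, 22.8 and 20.7 points respectively, against 23.2 unadjusted in the same simulation.
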